6.2 Safety Endpoints

The following safety endpoints will be assessed during treatment and the post-treatment/follow-up periods:

- Incidence of adverse events;
- Change in vital signs (including body temperature and dyspnoea);
- Change in 12-lead ECG parameters;
- Incidence of clinically or hemodynamically significant episodes of supraventricular or ventricular arrhythmias detected by continuous ECG dynamic monitoring;
- Change in laboratory parameters (hematology, blood chemistry and urinalysis);
- Change in renal function;
- Change in cTnT;
- Incidence of cTnT elevation relative (>50% or >20% relative increase over the cTnT levels at baseline, for patients with cTnT basal levels at baseline < or ≥ of the 99% URL (upper reference levels, as defined for the Roche hs test in patients with normal renal function, eGFR ≥ 85 ml/min); in patients with eGFR below this value, the renal function variations must be considered in evaluating the significance of the cTnT changes);

• Mortality at Day 30.

6.3 PK Parameters

After infusion, the following PK parameters will be measured and/or calculated for plasma E and Z isomers (when applicable) of istaroxime and its metabolites PST2915, PST2922, and PST3093, using the validated software WinNonLin® 5.2 or higher (Pharsight Corporation):

C_{max}: Maximum plasma concentration achieved after single dose

 t_{max} : Time to achieve C_{max}

AUC_{0-t}: Area under the concentration curve from administration to the last observed

concentration time t, calculated after single dose with the linear trapezoidal

method

 $AUC_{0-\infty}$: Area under the concentration/time curve extrapolated to infinity, calculated, if

feasible, as $AUC_{0-t} + C_t/\lambda_z$, where C_t is the last measurable drug concentration

 λ_z : Terminal elimination rate constant, calculated after single dose, if feasible, by

log-linear regression using at least 3 points

 $t_{1/2}$: Half-life, calculated, if feasible, as $ln2/\lambda_z$

MRT: Mean Residence time, calculated, if feasible, as AUMC_{0-\infty} / AUC_{0-\infty} - $t_i/2$,

where AUMC_{0-∞} is the area under the moment curve extrapolated to infinity

and t_i is the infusion duration

Cl_T: Total Body Clearance, calculated, if feasible, as Dose / AUC_{0-∞}

 V_z : Volume of distribution of the terminal phase calculated, if feasible as

Dose / (AUC_{0-\infty} x λ_z)

 V_{ss} : Volume of distribution at steady state calculated, if feasible as

(Dose x AUMC_{0- ∞}) / AUC_{0- ∞}²

The quality of log-linear regression (and, consequently, the reliability of the extrapolated PK parameters) should be demonstrated by a correlation coefficient $R^2 > 0.8$.

After infusion, the following PK parameters will be measured and/or calculated for urine E and Z isomers (when applicable) of istaroxime and its metabolites PST2915, PST2922, and PST3093, using the validated software WinNonLin® 5.2 or higher (Pharsight Corporation):

A_e: Total amount of analyte excreted in urine

A_e%: Percentage of analyte excreted in urine

Cl_R: Renal Clearance calculated, if feasible as A_e / AUC_{0-∞} (for istaroxime only)

These endpoints will be addressed in all the Italian patients and in a subset of Chinese patients.

Data below the lower quantification limit (LQL) will be considered as 0 in the calculations and presented as BLQL in listings and tables. As a consequence of BLQL (i.e. 0) values, calculated geometric means (if requested) could be null. For this reason, in the presence of any null value, the geometric mean will be reported as not calculated (NC).

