
Globally, istaroxime was well tolerated and safe up to 1.5 μg/kg/min in patients suffering from acute HF. Doses above 1.5 μg/kg/min were not completely tolerated due to *Protocol N°: CVT-CV-002*

gastrointestinal disorders and infusion site pain.

In conclusion, in this study the lowest tested dose of $0.5 \mu g/kg/min$ of istaroxime infused for 6 hours produces a significant PWCP improvement over placebo, being the istaroxime safety profile satisfactory even at higher dose, in this setting.

Pharmacokinetic results showed that istaroxime levels increased proportionally in plasma reaching steady state concentration within the 1hour infusion. Estimated half-life for istaroxime was about 10 to 20 minutes at infusion rates higher than 1.66 μ g/kg/min. For rates of infusion lower than 1.66 μ g/kg/min, concentration dropped below the limit of quantification (10 ng/ml) at 5 min after stopping of the infusion.

The systemic exposure to istaroxime resulted to be linearly related to the administered dose [20]. A very high clearance was shown, resulting around 4500 ml/min for a 70 kg body weight man. The concentration of PST 2915, the main metabolite (6β-alcholol) of the parent compound, was also measured, showing that its concentration slowly increased during infusion period, reaching a maximum concentration within 10 min after the stop of the intravenous infusion of istaroxime [20]. The metabolite maximum concentration resulted to be about one half of the corresponding C_{max} of istaroxime. Half-life of PST 2915 resulted to be around 3 to 4.5 hours [20]. PST 2915 resulted to be an active metabolite showing the same stimulatory activity on SERCA2a of istaroxime but about 10 time less inhibitory activity on Na-KATPase and potency in in vivo animal models than istaroxime [20].

For infusion longer than 1 hour, PST 2915 plasma concentrations increase with time, while those of istaroxime remain at steady state, being constant the rate of infusion.

To evaluate the risk of a prolongation of istaroxime intravenous infusion over six hours, pharmacokinetic, efficacy and tolerability clinical studies have to be carried out. The above clinical evidence indicates that istaroxime could be a future treatment option for patients with ADHF and a low cardiac output state.

More detailed clinical information can be found in the Investigator's Drug Brochure [20].

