7. STUDY PROCEDURES

♦ Screening period (between Hours -24 to -1)

Within a maximum of 24 hours before administration of study medication (istaroxime or placebo), a medical screening will be performed on all prospective patients to assess suitability for the study. Prior to conducting any study specific procedures, the investigator or his/her designee will explain the study fully to the patient and provide him/her with a copy of the Patient Information Sheet and Informed Consent Document. If the patient is willing to participate in the study, s/he and the investigator or his/her designee will both sign the Informed Consent Document and a copy of the signed document will be kept by the patient.

1) Obtaining of ICF;

- 2) Evaluation of screening inclusion and exclusion criteria;
- 3) Stratification: Atrial fibrillation YES/NO;
- 4) Medical history, demographic/anthropometric data;
- 5) Alcohol and tobacco consumption patterns;
- Medication history (previous and concomitant), including a list of the patient's previous and current intake of vitamins, over-the-counter drugs and herbal products for the last 3 months. Chronic oral treatment with digoxin and other medications (e.g. diuretic and/or vasodilator) will also be recorded;
- 7) Vital signs (including body temperature and dyspnea);
- 8) 12-lead ECG; (Data obtained within 3 hours before the patient signed informed consent form can be accepted.)
- 9) Holter ECG;

- 10) Standard blood chemistry and Standard haematology;
- 11) TSH, T3 and T4;
- 12) Estimated glomerular filtration rate (eGFR);
- 13) Digoxin assay;
- 14) Urinalysis;
- 15) Alcohol breath test (at random, if deemed necessary by the Investigator/designee);
- 16) Serum pregnancy test (beta human chorionic gonadotropin [β-hCG]) for females of childbearing potential;
- 17) Echocardiography;
- 18) Serum creatinine clearance;
- 19) Human Immunodeficiency Virus, Hepatitis B and Hepatitis C tests;
- 20) Adverse events monitoring (after obtaining informed consent);
- 21) BNP, NT-proBNP and cTnT;

♦ Treatment period (Day 1)

- 1) Confirm eligibility;
- 2) Randomization of patients (after eligibility has been confirmed);
- 3) Insertion of multiple lumen intravenous catheter (or administration via peripheral vein);
- 4) Start istaroxime or placebo infusion (date and time of infusion start must be recorded in the CRF);
- 5) cTnT (at pre-dose in two samples, 3, 6, 12, 24, 48 and 72 hours after start of infusion);

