- 6) NT pro-BNP at baseline and at the end of 24 hours infusion
- 7) Blood sample collection for metabolites and PK (at pre-dose, 0.5, 3, 6, 12, 24 hours after start of infusion and 0.25, 0.5, 1, 4, 12, 24, 48 hours after the end of infusion) in a subset of Italian patients and in a subset of Chinese patients pharmacokinetics and metabolism of istaroxime shall also be studied;
- 8) Vital signs (including arterial oxygen saturation and dyspnoea at pre-dose, 3, 6, 12 and 24 hours after the start of infusion);
- 9) 12-lead ECG profile (pre-dose, 3, 6, 12 hours and between 23 hours and 23 hours 55 minutes after infusion, totally 5 times, each time 3 measurements);
- 10)Stop 24-hour Holter ECG (Day -1 recording; Holter ECG monitor stops automatically 24 hours after the recording has been started;
- 11) Start 24-hour Holter ECG (Day 1 recording; to be started immediately before initiation of the study drug infusion);
- 12) Echocardiography at baseline and 6 and 24 hours after infusion start;
- 13) 24-hours urine collections for measurement of istaroxime and its metabolites and urinary

- creatinine for the calculation of the creatinine clearance
- 14) Blood collection for K+ and eGFR between 23 hours and 30 minutes and 23 hours and 55 minutes since infusion start
- 15) Concomitant medication monitoring (including chronic medication; dose, date and time must be recorded in the CRF);
- 16) Adverse events monitoring.

♦ Post-treatment period (Day 2 to Day 4)

Evaluations on Day 2 (end of the 24 hour infusion) include:

- 1) Vital signs (including arterial oxygen saturation and dyspnoea);
- 2) 12-lead ECG (triple ECGs) (between 23 hours and 23 hours 55 minutes since infusion start);
- 3) Stop 24-hour Holter ECG (Day 1 recording; to be stopped immediately after the end of study drug infusion;
- 4) Start 24-hour Holter ECG (Day 2 recording);
- 5) Stop istaroxime or placebo infusion (date and time of infusion end must be recorded in the CRF);
- 6) Serum potassium levels and 24-hour urine collection for measurement of istaroxime metabolites and urinary creatinine for calculation of the creatinine clearance;
- 7) Serum creatine clearance and calculation of eGFR;

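### Protocol 6.3 leaves the infusion-time term out of V_ss, so V_ss as written exceeds Cl_T × MRT by Cl_T × t_i/2 (about 3,240 L for a 24-hour infusion at 4.5 L/min)

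*Protocol*

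**What the plan says.** Protocol 6.3 (PK Parameters) defines these quantities together:

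- Cl_T = Dose / AUC0-∞.
- MRT = AUMC0-∞ / AUC0-∞ − t_i/2, "and t_i is the infusion duration".
- V_ss: "Volume of distribution at steady state calculated, if feasible as" (Dose × AUMC0-∞) / AUC0-∞². This has no infusion-time term.

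The section also sets a reliability condition for extrapolated parameters, which "should be demonstrated by a correlation coefficient" R² above 0.8, and requires at least three points for λz.

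The synopsis and Protocol 3 give the treatment as a continuous 24-hour i.v. infusion. On clearance, Protocol 1.2 reports a value "resulting around 4500 ml/min for a 70 kg body weight man". SAP 3.2 lists MRT, Cl_T and V_ss among the istaroxime plasma parameters but gives no formula. SAP 9.0 gives no PK-parameter code beyond a rank test for Tmax, and SAP 7.9 plans no other analyses. Protocol 6.3 is therefore the only definition of V_ss in the two documents.

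**The concern.** After a constant-rate infusion, AUMC/AUC contains the mean time the drug spends waiting to be infused, t_i/2, as well as the mean residence time. Protocol 6.3 removes that term for MRT and leaves it in for V_ss, so the section is inconsistent with itself.

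A V_ss calculated as written would depend on how long the infusion ran. With a planned t_i of 24 hours, and a drug the protocol describes as cleared rapidly, most of the reported volume would reflect infusion length and not distribution. It would contradict the MRT and Cl_T tabulated beside it. It would also mislead any comparison with the 1-hour and 6-hour infusions in Protocol 1.2. PK is a stated objective (Protocol 2), and Protocol 1.2 says that infusion beyond six hours still needs pharmacokinetic study.

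**Working it through.** The documents state no V_ss value, so there is no figure to reproduce. The check uses the protocol's own definitions.

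**Inputs**

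- Formulas for Cl_T, MRT and V_ss: Protocol 6.3.
- t_i = 24 h = 1,440 min, so t_i/2 = 720 min: synopsis and Protocol 3.
- Clearance about 4,500 ml/min = 4.5 L/min at 70 kg: Protocol 1.2.
- Half-life, for scale only: "Estimated half-life for istaroxime was about 10 to 20 minutes at infusion rates higher than 1.66" μg/kg/min (Protocol 1.2). Its use at 0.5 and 1.0 μg/kg/min is an assumption.

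**Step 1: identity**

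V_ss(stated) = Dose × AUMC / AUC² = (Dose/AUC) × (AUMC/AUC) = Cl_T × (MRT + t_i/2)

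V_ss(stated) − Cl_T × MRT = Cl_T × t_i/2

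No compartment model or half-life is used.

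**Step 2: size of the excess at 4.5 L/min**

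| Infusion ends at | t_i/2 (min) | Excess (L) |
|---|---|---|
| 24 h | 720 | 4.5 × 720 = 3,240 |
| 18 h | 540 | 4.5 × 540 = 2,430 |
| 12 h | 360 | 4.5 × 360 = 1,620 |
| 6 h | 180 | 4.5 × 180 = 810 |

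For assumed clearances of 3 to 6 L/min, the 24-hour excess runs from 3 × 720 = 2,160 L to 6 × 720 = 4,320 L.

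**Step 3: numerical check, one compartment, 24 h**

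Here MRT = half-life / ln 2, and AUC and AUMC are integrated numerically.

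| Assumed half-life | MRT (min) | Cl_T × MRT (L) | Stated V_ss (L) | Excess (L) | Ratio |
|---|---|---|---|---|---|
| 10 min | 14.4 | 64.9 | 3,304.9 | 3,240.0 | 50.9 |
| 20 min | 28.9 | 129.8 | 3,369.8 | 3,240.0 | 26.0 |

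Both doses give the same values. The ratio is (MRT + 720)/MRT, so it falls as MRT lengthens: (60 + 720)/60 = 13 and (120 + 720)/120 = 7.

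**Step 4: numerical check, two compartments**

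Assumed values are V1 60 L, V2 150 L and intercompartmental clearance 0.8 L/min, so the true V_ss is 210 L. The stated formula gives 3,450.0 L at 24 h (excess 3,240.0 L) and 1,830.0 L at 12 h (excess 1,620.0 L).

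**Step 5: the planned sampling times**

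This uses the Protocol 12 schedule up to 1 h after the end of infusion, linear trapezoids, one compartment, no quantification limit, and the true λz for extrapolation.

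| Assumed half-life | Estimated Cl_T (L/min) | Cl_T × MRT (L) | Stated V_ss (L) | Excess (L) | Ratio |
|---|---|---|---|---|---|
| 10 min | 4.532 | 96 | 3,359 | 4.532 × 720 = 3,263 | 35 |
| 20 min | 4.555 | 177 | 3,456 | 4.555 × 720 ≈ 3,279 | 20 |

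Sparse sampling narrows the ratio but does not remove the excess.

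**The case against.** The algebra is not in dispute. The objections concern whether the error reaches a reported number and how much would depend on it.

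*Feasibility.* This is the strongest point. At 4,500 ml/min and 70 kg, the steady-state concentration is 70 μg/min ÷ 4,500 ml/min = 15.6 ng/ml at 1.0 μg/kg/min, and 7.8 ng/ml at 0.5. In the earlier work, below 1.66 μg/kg/min, "concentration dropped below the limit of quantification (10 ng/ml) at 5 min after stopping of the infusion", and the first post-infusion sample here is at 15 minutes. If the 10–20 minute half-life held, quantifying the 0.25, 0.5 and 1 h samples would need a limit of about 0.24–1.9 ng/ml at the higher dose and 0.12–0.97 ng/ml at the lower. Counting the end-of-infusion sample as a terminal point relaxes this to about 1.9–5.5 and 0.97–2.8 ng/ml. With the earlier limit, λz could not be estimated at either dose, and V_ss would be missing along with Cl_T and MRT. The limit of this trial's assay is not given. So V_ss may be missing for many patients or for all of them. That bears on how many values are affected, not on whether the formula is right.

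*Software.* Protocol 6.3 names WinNonLin, and the documents do not show which V_ss expression or dosing setting would be used. A correct setting would give a correct value, but one that departs from the written definition. The text needs the same change either way.

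*Isomers.* Parameters are to be calculated for the E and Z isomers where applicable, and the 4,500 ml/min is not split by isomer. The 3,240 L is therefore an illustration at that clearance. The identity holds for each isomer at its own clearance.

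*Little depends on it.* This stands. V_ss is not among the parameters tested for dose linearity in Protocol 14.2, only a PK subset is involved, and efficacy, safety and escalation are untouched.

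**Conclusion.** The concern holds. V_ss as defined in Protocol 6.3 is wrong for an infusion and inconsistent with the MRT and Cl_T in the same section. The excess is exactly Cl_T × t_i/2. The figure of 3,240 L rests on the protocol's approximate 70 kg clearance and a full 24-hour infusion. The 26- to 51-fold ratios rest further on one compartment and on a half-life reported only at higher rates, and should be read as scale only.

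Confidence in the identity is high. The practical consequence is low, because V_ss is descriptive, may often not be estimable, and can be recovered as Cl_T × MRT wherever those two are reported. It should still be corrected, because the stated rule gives a wrong value whenever it is applied.

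**What to change.** In Protocol 6.3, and in any PK analysis specification, replace the V_ss formula with:

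V_ss = Cl_T × MRT = (Dose / AUC0-∞) × (AUMC0-∞ / AUC0-∞ − t_i/2)

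State that t_i is each patient's actual infusion duration and that Dose is the amount actually infused. The dose statement applies equally to Cl_T and V_z. Where the software's own V_ss output is used, confirm that it applies this infusion form.

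The cost is one formula line and a sentence of definition. No new data are needed. Protocol 7 already requires that the "date and time of infusion start must be recorded in the CRF" and that the "date and time of infusion end must be recorded in the CRF", and SAP 6.2 already derives exposure time from these entries.

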7. STUDY PROCEDURES

♦ Screening period (between Hours -24 to -1)

Within a maximum of 24 hours before administration of study medication (istaroxime or placebo), a medical screening will be performed on all prospective patients to assess suitability for the study. Prior to conducting any study specific procedures, the investigator or his/her designee will explain the study fully to the patient and provide him/her with a copy of the Patient Information Sheet and Informed Consent Document. If the patient is willing to participate in the study, s/he and the investigator or his/her designee will both sign the Informed Consent Document and a copy of the signed document will be kept by the patient.

1) Obtaining of ICF;

- 2) Evaluation of screening inclusion and exclusion criteria;
- 3) Stratification: Atrial fibrillation YES/NO;
- 4) Medical history, demographic/anthropometric data;
- 5) Alcohol and tobacco consumption patterns;
- Medication history (previous and concomitant), including a list of the patient's previous and current intake of vitamins, over-the-counter drugs and herbal products for the last 3 months. Chronic oral treatment with digoxin and other medications (e.g. diuretic and/or vasodilator) will also be recorded;
- 7) Vital signs (including body temperature and dyspnea);
- 8) 12-lead ECG; (Data obtained within 3 hours before the patient signed informed consent form can be accepted.)
- 9) Holter ECG;

- 10) Standard blood chemistry and Standard haematology;
- 11) TSH, T3 and T4;
- 12) Estimated glomerular filtration rate (eGFR);
- 13) Digoxin assay;
- 14) Urinalysis;
- 15) Alcohol breath test (at random, if deemed necessary by the Investigator/designee);
- 16) Serum pregnancy test (beta human chorionic gonadotropin [β-hCG]) for females of childbearing potential;
- 17) Echocardiography;
- 18) Serum creatinine clearance;
- 19) Human Immunodeficiency Virus, Hepatitis B and Hepatitis C tests;
- 20) Adverse events monitoring (after obtaining informed consent);
- 21) BNP, NT-proBNP and cTnT;

♦ Treatment period (Day 1)

- 1) Confirm eligibility;
- 2) Randomization of patients (after eligibility has been confirmed);
- 3) Insertion of multiple lumen intravenous catheter (or administration via peripheral vein);
- 4) Start istaroxime or placebo infusion (date and time of infusion start must be recorded in the CRF);
- 5) cTnT (at pre-dose in two samples, 3, 6, 12, 24, 48 and 72 hours after start of infusion);
- 6) NT pro-BNP at baseline and at the end of 24 hours infusion
- 7) Blood sample collection for metabolites and PK (at pre-dose, 0.5, 3, 6, 12, 24 hours after start of infusion and 0.25, 0.5, 1, 4, 12, 24, 48 hours after the end of infusion) in a subset of Italian patients and in a subset of Chinese patients pharmacokinetics and metabolism of istaroxime shall also be studied;
- 8) Vital signs (including arterial oxygen saturation and dyspnoea at pre-dose, 3, 6, 12 and 24 hours after the start of infusion);
- 9) 12-lead ECG profile (pre-dose, 3, 6, 12 hours and between 23 hours and 23 hours 55 minutes after infusion, totally 5 times, each time 3 measurements);
- 10)Stop 24-hour Holter ECG (Day -1 recording; Holter ECG monitor stops automatically 24 hours after the recording has been started;
- 11) Start 24-hour Holter ECG (Day 1 recording; to be started immediately before initiation of the study drug infusion);
- 12) Echocardiography at baseline and 6 and 24 hours after infusion start;
- 13) 24-hours urine collections for measurement of istaroxime and its metabolites and urinary

- creatinine for the calculation of the creatinine clearance
- 14) Blood collection for K+ and eGFR between 23 hours and 30 minutes and 23 hours and 55 minutes since infusion start
- 15) Concomitant medication monitoring (including chronic medication; dose, date and time must be recorded in the CRF);
- 16) Adverse events monitoring.

♦ Post-treatment period (Day 2 to Day 4)

Evaluations on Day 2 (end of the 24 hour infusion) include:

- 1) Vital signs (including arterial oxygen saturation and dyspnoea);
- 2) 12-lead ECG (triple ECGs) (between 23 hours and 23 hours 55 minutes since infusion start);
- 3) Stop 24-hour Holter ECG (Day 1 recording; to be stopped immediately after the end of study drug infusion;
- 4) Start 24-hour Holter ECG (Day 2 recording);
- 5) Stop istaroxime or placebo infusion (date and time of infusion end must be recorded in the CRF);
- 6) Serum potassium levels and 24-hour urine collection for measurement of istaroxime metabolites and urinary creatinine for calculation of the creatinine clearance;
- 7) Serum creatine clearance and calculation of eGFR;
- 8) cTnT (50% or 20% relative increase over the basal cTnT levels, respectively for patients with cTnT basal levels < or ≥ of the 99% URL (upper reference levels, as defined for the Roche hs test, in patients with normal renal function, eGFR≥85 ml/min); in patients with eGFR below this value, the renal function variations must be considered in evaluating the significance of the cTnT changes);
- 9) NT pro-BNP
- 10) Metabolites
- 11) Echocardiography;
- 12) Concomitant medication monitoring (including chronic medication must be recorded in the CRF);
- 13) Adverse Events monitoring

Evaluations on Day 3 include:

- 1) Vital signs (including arterial oxygen saturation and dyspnea)
- 2) 12-Lead ECG (single ECGs)
- 3) Stop 24-hour Holter ECG
- 4) Standard hematology;
- 5) Standard blood chemistry;
- 6) Serum Potassium levels;

- 7) 24-h urine collection for measurement of istaroxime metabolites and urinary creatinine for the calculation of creatinine clearance;
- 8) Calculation of eGFR;
- 9) NT-proBNP
- 10) cTnT;
- 11) Metabolites;
- 12) Echocardiography;
- 13) Adverse events monitoring;
- 14) Concomitant medication monitoring (including chronic medication must be recorded in the CRF)

Evaluations on Day 4 include:

- 1) cTnT and NT-proBNP (at 72 hours after start of infusion)
- 2) Vital signs (including arterial oxygen saturation and dyspnoea)
- 3) Physical examination (HF signs included)
- 4) 12-lead ECG
- 5) Adverse events monitoring
- 6) Concomitant medication monitoring (including chronic medication)
- 7) Metabolites (at 72 hours after start of infusion)
- 8) Serum potassium and creatinine levels for calculation of eGFR
- 9) Creatinine clearance

♦ Follow-up period and visit (Day 5 to Day 30)

During the follow-up period the Investigator/designee will make every effort to establish patient outcomes.

Evaluations on Day 30 (follow-up visit) include:

- 1) Vital signs (including arterial oxygen saturation and dyspnoea);
- 2) 12-lead ECG in triplicate;
- 3) Calculation of eGFR;
- 4) Standard hematology;
- 5) Standard blood chemistry;
- 6) NT-proBNP;
- 7) cTnT;
- 8) Urine pregnancy test (β -HCG) for females of childbearing potential;
- 9) Urinalysis;

- 10) Physical examination (HF signs included);
- 11) Adverse events monitoring;
- 12) Concomitant medication monitoring (including chronic medication).

